3. PLANNED ANALYSES

3.1. Interim Analyses

3.1.1. Interim Analysis for Part 2: Bayesian Predictive Adaptive Design for GBM Cohort

A Bayesian predictive adaptive design that allows the trial to be monitored more frequently at multiple stages [Lee, 2008] will employed for GBM cohort in Part 2 of the study. The criteria will be based on a historically unimportant six-month PFS rate of 17% versus a six-month PFS rate of interest of 35%. The six-month PFS rate is defined as the proportion of the subjects who are progression free and still alive at six months from the start of treatment. Bayesian statistics will be employed to calculate the posterior probability that the six-month PFS rate \geq 35% and \geq 17% at interim assuming a Beta prior for the Binomial distributed data. Predictive probability calculates the probability that the six-month PFS rate \geq 35% or \geq 17% given the responses have already been observed. A weak prior Beta (0.03, 0.07) is used, which is equivalent to the information present in 0.1 subject. The first interim analysis may be conducted when at least 10 evaluable subjects are available for GBM cohort at a given dose. The evaluable subjects for GBM cohort are defined as the GBM subjects who have had three post baseline disease assessments or have progressed or have died or have withdrawn from study treatment due to any reason. Futility interim analysis decision rules for the 10th to 27th evaluable subjects, specifying the number of subjects who have not progressed six months after receiving the first dose of GSK3326595 needed for continuing enrollment or stopping for futility when total sample size is up to 27 is presented in Table 4. These rules are intended as a guideline. Actual decisions will depend on the totality of the data.

Number of	Number progression-free at	Probability of declaring	Probability declaring
Evaluable	6 months to Stop Early for	futility when 6m PFS	futility when 6m PFS
Subjects	Futility	rate=0.17	rate=0.35
10	0	0.1552	0.0135
11	0	0.0000	0.0000
12	0	0.0000	0.0000
13	1	0.1817	0.0199
14	1	0.0000	0.0000
15	1	0.0000	0.0000
16	1	0.0000	0.0000
17	2	0.1325	0.0144
18	2	0.0000	0.0000
19	2	0.0000	0.0000

Table 4Decision Making Criteria for GBM Futility

Number of	Number progression-free at	Probability of declaring	Probability declaring
Evaluable	6 months to Stop Early for	futility when 6m PFS	futility when 6m PFS
Subjects	Futility	rate=0.17	rate=0.35
20	2	0.0000	0.0000
21	3	0.1004	0.0108
22	3	0.0000	0.0000
23	4	0.1125	0.0194
24	4	0.0000	0.0000
25	4	0.0000	0.0000
26	5	0.0799	0.0174
27	6	0.0869	0.0390

The enrollment for GBM cohort may be stopped due to futility if the predictive probability that the 6 month PFS rate $\geq 17\%$ (historical control) is small (e.g., less than a 2% chance for a total sample size of 28 subjects). Enrollment may also be stopped due to futility if the equivalent of all the evaluable subjects are progressed or off study treatment before 6 months from the first dose in the first 10 enrolled evaluable subjects in GBM cohort or less than 1 subject who is not progressed still on treatment at month 6 are observed in the first 13 evaluable subjects. For example, when there are 10 evaluable subjects available at the time of interim analysis with all subjects progressed before month 6, then the cohort may be stop for futility. Otherwise, the enrollment of the respective cohort will continue to the target sample size.

When the total sample size in a treatment arm is 28 and at least 8 subjects who are not progressed before 6 months from first dose and still on treatment at month 6 out of 28 subjects are observed, we can claim null hypothesis is rejected.

3.1.2. Interim Analysis for Part 2: Bayesian Hierarchical Modeling for mTCC, TNBC, and NHL Cohorts

To further investigate clinical activity across the pre-specified cohorts, an adaptive design utilizing a Bayesian hierarchical model will be employed for the mTCC, TNBC, p53 WT NHL and p53 mutant NHL cohorts in Part 2. [Berry, 2013; Escobar, 1995; Neal, 2000; Sethuraman, 1994] Multiple interim evaluations of the accumulating data to determine if one or more cohorts should discontinue enrollment early due to futility will be incorporated. Interim and final evaluations will be based on a hierarchical model that borrows information in a limited way from cohorts that demonstrate similar treatment effects based on the accumulated trial data. Traditional estimates based on independent analyses will also be provided. π_j is the true response rate for cohort *j*, where j = 1, ..., 4 and indexes the four cohorts. C_j is the historical control response rate for the jth cohort. The historical controls vary by cohort and are provided in Section 2.4. The study is powered to detect a high clinically meaningful response rate and is based on the cohort model assessment of whether there is sufficiently high probability that π_j exceeds C_j. The posterior probability that the ORR for a given cohort is greater than C_j will be computed according to the following comparison:

 $P \; (\pi_j \geq C_j \mid \text{current data}) \; \text{for the j-th cohort}$

If this posterior probability is sufficiently low within a given cohort, then this will provide insufficient evidence to suggest that the ORR is greater than its respective historical control. Conversely, if a sufficiently high posterior probability is observed, this will provide evidence that the ORR is greater than the historical control, and the dose will be declared efficacious in that cohort. Thresholds for decision making are defined in the protocol.

Full details regarding the hierarchical modeling framework are described in the protocol at Appendix 11.

3.1.3. Interim Analysis for Part 1 Cohorts and for ACC Cohort in Part 1 and Part 2

The purpose of this interim analysis is to summarize safety and efficacy endpoints within all Part 1 cohorts and the Part 1 and Part 2 ACC cohort for the purpose of publication. For Part 1 dosing cohorts, demographics, disease history, safety, treatment duration, percent change from baseline, best overall response, and PK will be summarized on the all-treated population. For ACC cohorts, best overall response, duration of follow-up, percent change from baseline, duration of treatment, and disease history will be summarized on the all-treated population, while progression-free survival will be summarized and plotted using the evaluable population.

3.1.4. Interim Analysis for Part 2: Simon's Two Stage Design for ACC Cohort

Simon's optimal two-stage design (Simon, 1989) will be used for both ACC cohorts (tablet and capsule formulation). For both cohorts, the null hypothesis that the true response rate is 10% will be tested against a one-sided alternative of 30%.

For the capsule cohort, in the first stage, 10 subjects will be accrued. If there are 1 or fewer responders in these 10 subjects, the cohort will be stopped early for futility. The maximum number of subjects to be enrolled for this cohort is 38. The null hypothesis will be rejected if 8 or more responders are observed in 38 patients. This design yields a type I error rate of 0.023 and power of 80.8% when the true response rate is 30%.

For the tablet cohort, in the first stage, 17 subjects will be accrued. If there are 2 or fewer responders in these 17 subjects, the cohort will be stopped early for futility. This rule is intended as a guideline, development decisions will depend on the totality of the data. The maximum number of subjects to be enrolled for this cohort is 50. The null hypothesis will be rejected if 10 or more responders are observed in 50 patients. This design yields a type I error of 0.02 and power of 89.9% when the true response rate is 30%.

3.1.5. Interim Analysis for Part 2: Bayesian Predictive Adaptive Design for ER+BC Cohort

The ER+BC cohort will employ the Bayesian design that allows the trial to be monitored frequently with the constraint of both Type I and Type II error rates. The evaluation is designed to exclude a 10% overall response rate (ORR) representing best available therapy in favour of a 25% ORR. A close to non-informative prior will be used. Let p

denote the response rate, the prior distribution used is $p \sim Beta (0.025, 0.075)$. The cohort will be stopped early due to futility if the predictive probability of success is less than 8%. The success is defined as posterior probability of ORR > 10% at the end of the cohort is larger than 80%. The first interim analysis will be performed when at least 10 subjects become evaluable. The max sample size is 35 subjects, and the design will have type I error of 0.10 and power of 82%.

The decision rules, specifying the number of subjects with a clinical response needed for continuing enrolment or, stopping for futility, are displayed in Table 5. The methodology is based on the predictive probability of success if enrolment continues to maximum number of subjects (Lee, 2008). The interim analysis will be for futility only, i.e., the dose expansion cohort will not stop early for efficacy.

	\leq This Number of	Probability of	Probability of
Number of Evaluable	Confirmed Responses to	continuing enrolling	continuing enrolling
Subjects	Stop Early for Futility	when ORR=0.1	when ORR=0.25
10	0	0.6513	0.9437
11	0	0.6513	0.9437
12	0	0.6513	0.9437
13	0	0.6513	0.9437
14	1	0.3971	0.8843
15	1	0.3971	0.8843
16	1	0.3971	0.8843
17	1	0.3971	0.8843
18	1	0.3971	0.8843
19	1	0.3971	0.8843
20	1	0.3971	0.8843
21	1	0.3971	0.8843
22	2	0.2938	0.8674
23	2	0.2938	0.8674
24	2	0.2938	0.8674
25	2	0.2938	0.8674
26	2	0.2938	0.8674
27	3	0.2108	0.8511
28	3	0.2108	0.8511
29	3	0.2108	0.8511
30	3	0.2108	0.8511
31	3	0.2108	0.8511
32	4	0.1509	0.8369
33	4	0.1509	0.8369
34	4	0.1509	0.8369

Table 5 Decision Making Criteria for ER+BC Futility

3.1.6. Interim Analysis for Part 2: Bayesian Predictive Adaptive Design for HPV+ Cohort

The HPV+ cohort will employ the Bayesian design that allows the trial to be monitored frequently with the constraint of both Type I and Type II error rates. The evaluation is designed to exclude a 10% overall response rate (ORR) representing best available therapy in favour of a 30% ORR. A close to non-informative prior will be used. Let p denote the response rate, the prior distribution used is $p \sim Beta (0.03, 0.07)$. The cohort will be stopped early due to futility if the predictive probability of success is less than 1%. The success is defined as posterior probability of ORR > 10% at the end of the cohort is larger than 87.6%. The first interim analysis will be performed when at least 10 subjects become evaluable. The max sample size is 28 subjects, and the design will have type I error of 0.05 and power of 87%.

The decision rules, specifying the number of subjects with a clinical response needed for continuing enrolment or, stopping for futility, are displayed in Table 6. The methodology is based on the predictive probability of success if enrolment continues to maximum number of subjects (Lee, 2008). The interim analysis will be for futility only, i.e., the dose expansion cohort will not stop early for efficacy.

	\leq This Number of	Probability of	Probability of
Number of Evaluable	Confirmed Responses to	continuing enrolling	continuing enrolling
Subjects	Stop Early for Futility	when ORR=0.1	when ORR=0.3
10	0	0.6513	0.9718
11	0	0.6513	0.9718
12	0	0.6513	0.9718
13	0	0.6513	0.9718
14	0	0.6513	0.9718
15	0	0.6513	0.9718
16	0	0.6513	0.9718
17	1	0.4660	0.9618
18	1	0.4660	0.9618
19	1	0.4660	0.9618
20	1	0.4660	0.9618
21	2	0.3107	0.9500
22	2	0.3107	0.9500
23	2	0.3107	0.9500
24	2	0.3107	0.9500
25	3	0.2019	0.9383
26	3	0.2019	0.9383
27	4	0.1129	0.9161

Table 6 Decision Making Criteria for HPV+ Futility

3.1.7. Interim Analysis for Part 2: Statistical Design for NSCLC Cohort

The Part 2 NSCLC cohort is intended to explore the clinical activity in the p53 wild-type NSCLC population. Simon's optimal two-stage design will be used as a basis for analysis of the NSCLC cohort. The null hypothesis that the true response rate is 10% will be tested against a one-sided alternative. ORR will be assessed for the 10 subjects that are confirmed with p53 wild-type.

In the first stage, 10 subjects will be accrued. If there are 1 or fewer responders in the first 10 subjects, the cohort will be stopped for futility. If 2 or more responses are observed, further expansion of the p53 wild-type NSCLC cohort may be triggered via protocol amendment or as a part of another study. If the cohort were to expand to 29 subjects, the null hypothesis would be rejected if 6 or more responders are observed. This design yields a type I error rate of 0.047 and power of 80.5% when the true response rate is 30%.

Note that at the time GSK made a decision to cease enrollment in the study, this cohort did not have 10 subjects. Therefore, the interim analysis was not conducted.

3.1.8. Food Effect and Relative Bioavailability Sub-study

This analysis is described in Section 9.2.2.2.

3.1.9. Interim Analysis for Part 2: Statistical Design for All Part 2 Cohorts

The purpose of this interim analysis is to summarize safety and efficacy endpoints within all Part 2 cohorts for purposes of publication. Efficacy endpoints for TNBC, mTCC, ER+BC, HPV+, ACC, and NSCLC cohorts will be investigator-assessed confirmed, best response based on RECIST 1.1 criteria. For NHL cohorts, investigator-assessed best response based on Lugano criteria will be reported. See Section 7.1 for further details on criteria. For these groups, overall response rate (ORR) defined as the proportion of subjects with complete response (CR) or partial response (PR) with 95% confidence interval based on the Clopper-Pearson (1934) exact methods will be reported. In addition, frequency of best responses will also be reported by histology subtype for the NHL cohorts. For GBM, progression-free survival rate at 6 months will be reported, with a 95% confidence interval estimated using Greenwood's estimate of standard error.

Additional endpoints examined will be duration of treatment with best response for all cohorts. maximum percent reduction from baseline in sum of diameters as well as change from baseline for TNBC, mTCC, ER+BC, HPV+, ACC, and NSCLC cohorts, and maximum percent reduction from baseline in sum of areas for the GBM cohort.

In addition, safety parameters will be reported by dosage type (300 mg, 400 mg). Included will be a summary of adverse events, adverse events related to GSK3326595 by preferred term and by maximum grade, as well as adverse events leading to dose reduction, interruptions/delays, discontinuation and serious adverse events by preferred term, and summary of deaths.

3.3. Final Analyses

The final analysis of the study will be performed after the completion of the following sequential steps: As per Protocol Amendment 8 implementation, final analysis will be performed following the data cut off (DCO). This will occur when all subjects have either died, discontinued treatment (including 30-day safety follow up), withdrawn consent, or have consented to continue with treatment as defined in Protocol Amendment 8.

All required database cleaning activities have been completed and final database release (DBR), source data lock (SDL) and database freeze (DBF) have been declared by Data Management.

Data from the three parts may be combined for some analyses at the end of the trial, as appropriate. All primary and secondary analyses will be conducted for the final analysis.

4. ANALYSIS POPULATIONS

4.1. List of Populations

Population	Definition / Criteria	Analyses Evaluated
Screened	All participants who were screened for eligibility	Study Population
Enrolled	All participants who signed the ICF	Study Population
All Treated	Defined as all subjects who receive at least one dose of GSK3326595.	Safety Anti-cancer activity Efficacy (final analysis)
All Evaluable	For Part 1: Defined as subjects who have had any post-baseline response data, or who discontinued without any response data collected. For Part 2: Defined as subjects who have had	Interim Analysis
	two post baseline disease assessments, have progressed or died, or permanently discontinued from the study treatment for mTCC, TNBC, ER+BC, HPV+, NHL and NSCLC cohorts. It is defined as subjects who have had three post baseline disease assessments, have progressed or died, or permanently discontinued from the study treatment for ACC and GBM cohorts.	

Table 7Analysis Populations

Population	Definition / Criteria	Analyses Evaluated
Pharmacokinetic (PK)	Consist of all subjects from the All Treated Population for whom a PK sample is obtained and analyzed. Note: PK samples that may be affected by protocol deviations will be reviewed by the study team to determine whether or not the sample will be excluded.	PK
Pharmacodynamic (PD)	Defined as subjects in the All Treated Subjects Population for whom paired and evaluable tumor biopsies (pre- and on- treatment time points) or plasma or urine were obtained and analyzed for biomarkers.	PD

Refer to Appendix 12: List of Data Displays which details the population used for each display. Note that for the interim analyses, the All Evaluable population will be used for efficacy analyses, and the All-Treated Population will be used for safety analyses. However, for the final analysis, the All Treated Population will be used for all displays.

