5.3. Screening/Baseline/Run-in Failures

Screen failures are defined as subjects who consent to participate in the clinical trial but are never subsequently enrolled. In order to ensure transparent reporting of screen failure subjects, meet the Consolidated Standards of Reporting Trials (CONSORT) publishing requirements, and respond to queries from Regulatory authorities, a minimal set of screen failure information is required including Demography, Screen Failure details, Eligibility Criteria, and any Serious Adverse Events.

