6.2. Disposition of Subjects

A summary of the number of subjects in each of the analysis populations described in Section 4 will be provided. In addition, the number of subjects enrolled will be summarized by country and by center. In addition, a listing of subjects excluded from any analysis population will also be provided.

A summary and listing of screening status and reasons for screen failure will be provided using the Screened population.

A summary of subject status and reason for study withdrawal will be provided. This display will show the number and percentage of subjects who completed the study, are ongoing as of the analysis cutoff date, or withdrew from the study, including primary reasons for study withdrawal. Reasons for study withdrawal will be presented in the order they are displayed in the eCRF. A listing will also be provided.

A summary of study treatment status will be provided. This display will show the number and percentage of subjects who are ongoing or have discontinued study treatment and a summary of the primary reasons for discontinuation of study treatment. Reasons for study treatment discontinuation will be presented in the order they are displayed in the eCRF. A listing of study treatment discontinuation will be generated. The listing will include last dose date, and reasons for study treatment discontinuation.

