15.12.4. Study Population Tables

	_	IDSL / Example			
No.	Population	Shell	Title	Programming Notes	Deliverable
Subjec	t Disposition				
1.1	All Treated	ES8	Summary of Subject Status and Subject Disposition for the Study Conclusion Record	ICH E3, FDAAA, EudraCT To use the following from ES1 shell : "Outcome of Adverse Events Which Led to Study Withdrawal" with "NON-FATAL" and "FATAL" options. Add overall column. Part 1 by dose level, Part 2 by cohort, Part 3 by dose	SAC
1.2	All Treated	SD1	Summary of Treatment Status and Reasons for Discontinuation of Study Treatment (GSK3326595)	ICH E3 include footnote [1] and [2] from standard, but remove footnote [3] use same mock as created for ACC IA, Part 1 by dose level, Part 2 by cohort, Part 3 by dose	IA, SAC
1.3	All Treated	SD1	Summary of Treatment Status and Reasons for Discontinuation of Study Treatment (Pembrolizumab)	ICH E3 include footnote [1] and [2] from standard, but remove footnote [3] use same mock as created for ACC IA, Part 3	IA, SAC
1.4	Screened	ES6	Summary of Screening Status and Reasons for Screen Failure	Journal Requirements	SAC
1.5	Enrolled	NS1	Summary of Number of Participants by Country and Site ID (Enrolled Population)	EudraCT/Clinical Operations, Part 1 by dose level, Part 2 by cohort, Part 3 by dose	SAC
Protoc	ol Deviation	•	· · · · · · · · · · · · · · · · · · ·		
1.7	All Treated	DV1	Summary of Important Protocol Deviations	ICH E3, Part 1 by dose level, Part 2 by cohort, Part 3 by dose	SAC
Analys	is Populations				
1.8	Screened	SP1A	Summary of Study Populations	IDSL To include Enrolled, All Treated, PK, Evaluable (if diff from enrolled), PD, Part 1 by dose level, Part 2 by cohort, Part 3 by dose	IA, SAC
1.9	All Treated	SP2A	Summary of Exclusions from the Safety Population	IDSL Only if we have exclusions (i.e. food effect subjects?), Part 1 by dose level, Part 2 by cohort, Part 3 by dose	SAC
Demog	raphic and Bas	eline Characte	ristics		
1.10	All Treated	DM1	Summary of Demographic Characteristics	ICH E3, FDAAA, EudraCT, Part 1 by dose level, Part 2 by cohort, Part 3 by dose	IA, SAC
1.11	Enrolled	DM11	Summary of Age Ranges	EudraCT	SAC

		IDSL / Example			
No.	Population	Shell	Title	Programming Notes	Deliverable
Diseas	e Characteristic	S	•	• • • • • •	
1.12	All Treated	DC1	Summary of Disease Characteristics at Initial Diagnosis	ICH E3 Make note of separate CRF page for NHL subjects, Part 1 by dose level, Part 2 by cohort, Part 3 by dose	IA, SAC

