15.12.11. ICH Listings

		IDSL / Example			
No.	Population	Shell	Title	Programming notes	Deliverable
Participa	ant Disposition				_
1	All Treated	ES2	Listing of Reasons for Study Withdrawal	ICH E3 Part 1 (by dose), Part 2 (by cohort), Part 3 (by dose)	SAC
2	All Treated	SD2	Listing of Reasons for Study Treatment Discontinuation	ICH E3 Part 1 (by dose), Part 2 (by cohort), Part 3 (by dose)	SAC
84	Enrolled	TBD	Listing of Participants by Country and Site	ICH E3 IDSL Part 1 (by dose), Part 2 (by cohort), Part 3 (by dose)	SAC
Protoco	I Deviations				
3	Enrolled	DV2	Listing of Important Protocol Deviations	ICH E3 Report all important PDs Part 1 (by dose), Part 2 (by cohort), Part 3 (by dose)	SAC
4	All Treated	IE3	Listing of Participants with Inclusion/Exclusion Criteria Deviations	ICH E3 Part 1 (by dose), Part 2 (by cohort), Part 3 (by dose)	SAC
Analysis	S Populations				
5	Enrolled	SP3	Listing of Participants Excluded from All Treated Population	ICH E3 Report participants enrolled but not treated Part 1 (by dose), Part 2 (by cohort), Part 3 (by dose)	SAC
Demogr	aphic and Basel	ine Characteristics			
6	All Treated	DM2	Listing of Demographic Characteristics	ICH E3 Part 1 (by dose), Part 2 (by cohort), Part 3 (by dose)	SAC
7	All Treated	DM9	Listing of Race	ICH E3 Part 1 (by dose), Part 2 (by cohort), Part 3 (by dose)	SAC
Exposu	re				
8	All Treated	EX3	Listing of Exposure Data	ICH E3 should be able to include both GSK3326595 and pembrolizumab in the same listing. Add column for treatment. Note: only part 3 subjects will have pembro. Part 1 (by dose), Part 2 (by cohort), Part 3 (by dose)	SAC
Adverse	Events, and Sei	rious Adverse Ever	nts		
10	All Treated	AE8	Listing of All Adverse Events	ICH E3 Part 1 (by dose), Part 2 (by cohort), Part 3 (by dose)	SAC

	_	IDSL / Example			
No.	Population	Shell	Title	Programming notes	Deliverable
11	All Treated	AE7	Listing of Subject Numbers for Individual Adverse Events	ICH E3 Part 1 (by dose), Part 2 (by cohort), Part 3 (by dose)	SAC
12	All Treated	AE8	Listing of Non-Fatal Serious Adverse Events	ICH E3 Part 1 (by dose), Part 2 (by cohort), Part 3 (by dose)	SAC
13	All Treated	AE14	Listing of Reasons for Considering as a Serious Adverse Event	ICH E3 Part 1 (by dose), Part 2 (by cohort), Part 3 (by dose)	SAC
14	All Treated	AE8	Listing of Adverse Events Leading to Permanent Discontinuation of GSK3326595	ICH E3 Part 1 (by dose), Part 2 (by cohort), Part 3 (by dose) To include Permanent Discontinuation or Withdrawal in action taken	SAC

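### The SAP's Enrolled population takes in every screen failure, contrary to protocol 5.3, so two EudraCT tables and three listings would include people the protocol says were never enrolled

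*SAP*

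**What the plan says.** SAP 4.1, Table 7, lists two populations upstream of All Treated. Screened is "All participants who were screened for eligibility". Enrolled is "All participants who signed the ICF". The Enrolled definition does not require passing screening, being allocated to a part or cohort, or being dosed.

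Protocol 5.3 draws the line elsewhere: "Screen failures are defined as subjects who consent to participate in the clinical trial but are never subsequently enrolled". It also says what is held on these people: "a minimal set of screen failure information is required including Demography, Screen Failure details, Eligibility Criteria, and any Serious Adverse Events".

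SAP 6.2 promises that "the number of subjects enrolled will be summarized by country and by center". Appendix 12 implements this as Table 1.5, titled "Summary of Number of Participants by Country and Site ID (Enrolled Population", with the programming note "EudraCT/Clinical Operations, Part 1 by dose level, Part 2 by cohort, Part 3 by dose". Appendix 12 also names Enrolled as the population for Table 1.11 (age ranges, noted for EudraCT), Listing 3 (important protocol deviations), Listing 5 (participants excluded from All Treated, with the note "Report participants enrolled but not treated") and Listing 84 (participants by country and site). All five are final deliverables.

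The paragraph after Table 7 refers the reader to Appendix 12 for the population of each display. It then closes by saying that the final analysis uses All Treated for every display.

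**The concern.** The two documents use the same word for different sets of people. Under the protocol no screen failure is enrolled; under the SAP every screen failure is. SAP 2.1, which records departures from the protocol's planned analysis, does not mention this one.

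The number enrolled is a basic disclosed quantity, and here its breakdown by country, site and age band is prepared for EudraCT. If screen failures are counted, the reported number enrolled is too large by the protocol's own definition. The age distribution then describes a mixture of participants and people who never took part. Listing 5 has a specific job: to show who entered the study and did not receive drug. If every screen failure appears there, the few cases of interest have to be picked out by cross-reference.

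Protocol 5.3 gives transparent reporting of screen failures as its reason for collecting the minimal data set. Folding them into Enrolled works against that purpose.

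**Working it through.** Neither document states an enrolled count or a screen-failure count, so there is no figure to reproduce. The check compares definitions and then traces them to the displays.

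**Step 1: the sets.** Let C be everyone who signed the consent form and F the screen failures.
- Protocol 5.3: F lies inside C, and nobody in F is enrolled. Enrolled (protocol) = C minus F.
- SAP Table 7: Enrolled (SAP) = C.
- Difference: Enrolled (SAP) minus Enrolled (protocol) = F, that is, every screen failure.

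In the time and events tables consent is part of the screening visit, so the SAP's Enrolled and Screened populations nearly coincide.

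**Step 2: where the difference lands.**
- Table 1.5 and Listing 84: country and site counts are raised by the screen failures at each site.
- Table 1.11: protocol 5.3 requires demography for screen failures, so their ages are available and would enter the age bands.
- Listing 3: it would take in important deviations recorded for screen failures, if there are any.
- Listing 5: its content is Enrolled minus All Treated. Under the SAP definition that is F plus those enrolled in the protocol's sense but never dosed. Only the second group fits the listing's purpose.
- Table 1.8 runs on Screened but shows the Enrolled count as one of its rows. That row is affected in the same way.

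**Step 3: signs of what was intended.** The note to Table 1.8 asks for the Evaluable count only if it differs from Enrolled. That condition makes little sense if Enrolled contains every screen failure. The note to Listing 5 points the same way. Both fit the protocol's meaning, so Table 7 looks like a wording slip, but it is the governing definition.

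**Step 4: what is not touched.** Efficacy and safety displays use All Treated at the final analysis. At the interims SAP 4.1 uses All Evaluable for efficacy and All Treated for safety. None uses Enrolled.

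**Step 5: illustration of size, on assumed rates.** If s is the share of consenting people who fail screening and N is the number enrolled in the protocol's sense, the SAP count is N/(1 − s) and the excess is N/(1 − s) − N. Protocol Appendix 13 gives 270 treated as of 04 February 2021. Taking that as a stand-in for N:

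| assumed s | N/(1 − s) | excess | excess as % of N |
|---|---|---|---|
| 10% | 300 | 30.0 | 11% |
| 20% | 338 | 67.5 | 25% |
| 30% | 386 | 115.7 | 43% |

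The rates are assumptions, and 270 is an interim count of treated subjects. The table shows how the excess scales and does not estimate it.

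**The case against.** The strongest reply is the closing sentence of SAP 4.1, which puts every final display on All Treated. Read literally, no final table would contain a screen failure. SAP 6.1 also makes All Treated the default for study population displays, though only unless otherwise specified. The literal reading does not work. The same paragraph defers to Appendix 12, which names Enrolled for the five displays, and the title of Table 1.5 itself names the Enrolled population. Applied literally, the sentence would empty Listing 5 and override Tables 1.4 and 1.8 and Listing 23, which run on Screened, and the pharmacokinetic displays, which run on the PK population. It is a second inconsistency to correct.

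Other parts of the reply stand, and they limit how far the point can be taken:
- A reader might infer that loss before first dose cannot be recovered. It can, in total: Table 1.4 gives screening status and Table 1.8 gives the population counts, so Screened minus screen failures minus All Treated yields it. Listing 23 identifies the screen failures.
- A reader might infer that screen failures cannot be placed in the dose and cohort columns of Table 1.5. The documents do not establish that. Listing 23, the screen-failure listing, is itself to be shown by dose or cohort.
- A reader might expect the inflated count to be exposed by failing to match planned enrolment. The planned numbers are estimates and maxima, and recruitment was stopped, so no match is expected anyway.
- Disclosure does not rest on Enrolled alone. Tables 1.1 and 1.10, also marked for EudraCT, run on All Treated.

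Protocol 4.4.4 mentions late screen failures when it allows a sixth Part 3 subject to be enrolled, which is looser usage. Section 5.3 is the formal definition.

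**Conclusion.** The point holds as a contradiction of definition that reaches final displays. As the SAP stands, Tables 1.5 and 1.11 and Listings 3, 5 and 84 would include screen failures, and Listing 5 would list all of them. The excess in the enrolled count equals the number of screen failures, which the documents do not give; the percentages above depend entirely on assumed rates. This conclusion rests on Appendix 12 governing the population of each display, as SAP 4.1 says it does.

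It would be too much to conclude that any study result changes. No efficacy or safety result depends on Enrolled. Nor do the documents show that wrong numbers were produced, since programmers may have followed the evident intent of Table 1.8 and Listing 5. What they show is that the written rule gives wrong enrolled counts and age ranges. It is worth correcting because the outputs are for disclosure and the correction is small.

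**What to change.** In SAP 4.1, Table 7, define Enrolled as participants who signed the consent form and are not screen failures under protocol 5.3. State that anyone enrolled or treated despite an eligibility deviation remains Enrolled. Keep Screened for all participants who consented and were screened. Tables 1.5 and 1.11 and Listings 3, 5 and 84 then run on the corrected population without further change.

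Two alternative wordings should be avoided. Requiring that all eligibility criteria were met would drop treated subjects with inclusion or exclusion deviations, which SAP 4.2 and Listing 4 expect, so Enrolled would no longer contain All Treated. Relying on registration would not separate the groups, because registering the subject is a screening-visit item in protocol Tables 9, 14 and 15.

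In the paragraph after Table 7, limit the closing sentence on All Treated to efficacy and safety displays so that it agrees with Appendix 12.

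The cost is a redefined line, a narrowed sentence and one flag in the subject-level dataset. The reported enrolled number becomes smaller.
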